5.0 SUBJECT ELIGIBILITY

5.1 Inclusion Criteria

5.1.1 Any patient with non-APL acute leukemia (AML, ALL, biphenotypic leukemia) undergoing curative intent chemotherapy

OR

Any patient undergoing allogeneic HSCT for a hematologic disorder (including acute leukemia as above, CML, CLL, MDS, primary or secondary myelofibrosis, hypereosinophilic syndromes, plasma cell disorders, B-cell or T-cell lymphoma)

5.1.2 Disease may be measurable or non-measurable

5.1.3 Age \geq 18 years of age

5.1.4 Diagnosis of, symptomatic venous thromboembolism requiring therapeutic-dose anticoagulation (unfractionated or low-molecular weight heparin or oral anticoagulants) throughout the period of hematopoietic recovery.

5.1.5 Anticipated platelet count $\leq 50 \times 10^9/L$ for ≥ 5 days within 72 hours of enrollment

5.1.6 Ability to understand and the willingness to sign a written informed consent document

5.2 Exclusion Criteria

5.2.1 Separate episode of VTE or arterial thrombosis within 3 months of enrollment

5.2.2 Major bleed (WHO Grade 3 or 4) within 6 months of enrollment

5.2.3 Active bleeding (Grade 2 or higher) at the time of enrollment

5.2.4 History of intracranial bleeding at any time

5.2.5 Disorders of hemostasis including von Willebrand Disease, hemophilia, platelet function disorders

5.2.6 Concomitant use of aspirin or non-steroidal anti-inflammatory drugs

5.2.7 Evidence of disseminated intravascular anticoagulation (DIC) as determined by the patient's primary provider.

5.2.8 History of alloimmunization (defined as platelet refractoriness with PRA $>25\%$) at the time of or prior to enrollment

5.2.9 Uncontrolled or concurrent illness including, but not limited to, ongoing or active infection, unstable angina pectoris.

5.2.10 Psychiatric illness/social situations that would limit compliance with study requirements.

5.2.11 Pregnant or able to become pregnant and unwilling to use two forms of birth control during the study period

6.0 Subject Registration

Subjects will be identified either by patient care teams or by study personnel and then approached by study personnel following discussion with the patient's attending physician. To complete the registration process, the PI, Fred Hutch/UW Study Coordinator or designee will assign a patient study number, register the patient on the study, and enter the patient into the Protocol Accrual Tracking System (PATS). A complete, signed, study consent and HIPAA consent are required for registration.

7.0 Treatment Plan

This study is a single-center, open-label randomized pilot study of a platelet transfusion threshold of $30 \times 10^9/L$ vs $50 \times 10^9/L$ among patients receiving anticoagulation for, symptomatic VTE during periods of thrombocytopenia related to the treatment of hematologic malignancies at the Fred Hutchinson Cancer Research Center/University of Washington Seattle Cancer Care Alliance.

7.1 Treatment Plan Overview

In this pilot study, patients meeting the inclusion/exclusion criteria and their primary hematologists are asked whether or not they would agree to participate in the randomized treatment assignment (Appendix 1). Patients agreeable to randomization will be assigned in a 1:1 ratio to a higher ($50 \times 10^9/L$) or lower ($30 \times 10^9/L$) platelet transfusion threshold. For those who wish not to be randomized the reason to decline randomization will be recorded, and patients will be managed according to the discretion of their primary hematologist.

7.2 Baseline/Pre-Treatment Assessment

The following procedures will be obtained at baseline before randomization to establish trial eligibility and allow patient characterization. Results of tests and/or procedures conducted as per standard of care will be used to determine study eligibility.

- Medical history including disease and treatment specifics of both the hematologic malignancy and the venous thrombosis, history of bleeding and anti-thrombotic therapy including anticoagulation and antiplatelet agents.
- Targeted physical exam for evidence of bleeding, thrombosis and volume status
- Most recent complete blood counts (assessed within 3 days of study day 0)
- Most recent coagulation assays, including PT, PTT (within one week of study day 0) and fibrinogen (if available).
- CT scan, V/Q scan, Doppler ultrasound or other appropriate diagnostic modality to document VTE diagnosis.

7.3 Randomization

Randomization may be obtained after or up to 72 hours before the platelet count drops below $50 \times 10^9/L$, as long as the period of thrombocytopenia (platelet count $< 50 \times 10^9/L$ in the absence of platelet transfusion support) is anticipated to last for ≥ 5 days. Following randomization, patients will receive platelet transfusions on all days when the morning platelet count is below the threshold to which they have been randomized. Platelet counts should be checked according to standard of care (daily while inpatient, ≥ 3 times per week while outpatient).

7.4 Administration of Transfusions

The decision to administer a platelet transfusion will be based upon the first platelet count of the day (whether inpatient or outpatient). Transfusions will be administered when the count is below the randomized threshold and will be administered according to institutional policy. Post-transfusion counts will not be routinely checked unless there is reasonable expectation on the part of the subject's primary providers that a single transfusion will be insufficient to achieve a platelet count greater than the specified transfusion threshold. This would include a pre-transfusion platelet count $> 25 \times 10^9/L$ below the transfusion threshold or suspicion of alloimmunization or other platelet refractory state. If the post-transfusion check is below the specified threshold, an additional transfusion will be given. In the instance that a morning

platelet count is above the designated threshold and a repeat count, performed later in the day for clinical reasons (eg prior to a procedure), is below the threshold, transfusion is allowed at that time. Counts should not be repeated in a patient not meeting transfusion criteria on morning labs in the absence of another clinical indication.

Transfusions may be either single-donor apheresis units or pooled units, depending on availability and the clinical situation. Type and volume of each transfusion will be documented.

7.5 Concomitant Medication and Supportive Care Guidelines

Pre-medications, including acetaminophen, diphenhydramine and hydrocortisone may be administered in patients with a history of transfusion reaction. In the event of a new, suspected transfusion reaction, supportive care should be administered urgently according to institutional protocol and/or the discretion of the treating provider.

Therapeutic anticoagulation should be given with one of the following agents/dosing strategies.

7.5.1 Unfractionated heparin (UFH)

Heparin should be administered intravenously and may be given with or without a loading bolus(80 units/kg). The initial infusion should be 18 units/kg/hr and should be titrated according to a goal PTT of 60-100 seconds. Re-bolus for low PTT may be given at provider discretion (<https://depts.washington.edu/anticoag/home/content/heparin-infusion-guidelines>).

7.5.2 Low molecular weight heparin (LMWH)

LMWH may be administered either as enoxaparin or dalteparin. Enoxaparin should be administered at a dose of 1mg/kg subcutaneously every 12 hours for the first 30 days following diagnosis of VTE, after which dosing may be reduced to 1.5mg/kg daily. Dalteparin should be administered at a dose of 200 units/kg for a minimum of 30 days following diagnosis of VTE, after which dosing may be reduced to 150 units/kg daily.

7.5.3 Anticoagulation Dosing Modifications

Dosing modifications may be made to the above regimens for low body weight, obesity, or renal impairment according to the appropriate algorithms found at <https://depts.washington.edu/anticoag/home/>.

If temporary discontinuation of anticoagulation or reduction to prophylactic dosing is considered to be necessary by the treating provider (such as in the peri-operative or peri-procedure setting), these changes may be made at the provider's discretion for up to a 72 hour period. If anticoagulation must be held or given at a lower dose for longer than 72 hours, randomization will be broken and transfusions will be administered at the discretion of the managing provider(s). The new threshold and anticoagulation regimen will be noted and the patient will be followed for outcomes until the conclusion of a 30-day period from the date of randomization.

7.6 Transfusion Delays/Modifications

The transfusion threshold may be temporarily increased (for up to 72 hours) if a higher platelet count is required for safety in the setting of a procedure (including lumbar puncture and central

line placement). Transfusions according to the randomized threshold should resume once the procedure has been completed and bleeding risk has returned to baseline as determined by the proceduralist and/or the subject's primary provider.

Transfusion thresholds may also be temporarily increased for minor bleeding events which do not meet criteria for grade 3 or 4 bleeding but are bothersome to the patient (e.g. brief but recurrent episodes of epistaxis, vaginal bleeding). If benefit is achieved and the patient or provider feel an increased transfusion threshold is required beyond 72 hours, or if this occurs on three or more occasions during the study period, randomization will be broken and transfusions will be administered at the discretion of the managing provider(s). The new threshold will be noted and the patient will be followed for outcomes until the conclusion of a 30-day period from the date of randomization.

If post-transfusion thresholds are checked and patients are noted to be platelet refractory (defined as a $<5 \times 10^9/L$ increase in platelet count 30 minutes following a transfusion on ≥ 2 occasions) efforts should be made, according to institutional protocol and at the discretion of the provider, to optimize transfusion strategy, including the use of HLA-matched units, if necessary. If the subject remains refractory, despite all available interventions, and unable to achieve the targeted platelet threshold, the decision to continue or withhold anticoagulation will be made at the discretion of the primary provider and the patient will break randomization and be taken off protocol.

Possible reasons for transfusion delay include need for specific (eg HLA-matched in the instance alloimmunization develops during the study period) platelets which may not be immediately available or lack of resources (ie infusion room beds or nurses). A delay of no more than 24 hours will be acceptable in either case. Should matched platelets not be available for a period > 24 hours, pooled platelets should be administered. If matched platelets are unavailable for >48 hours and/or frequently unavailable the patient will break randomization and be taken off protocol. Anticoagulation may be continued or discontinued according to the managing provider.

7.7 Duration of Therapy

Patients will remain on protocol until (1) the platelet count spontaneously recovers to $>50 \times 10^9$ for three consecutive days, in the absence of transfusions or (2) for a maximum of 30 days after the date of randomization, whichever is shorter. The study period is defined as the period between the first on-study day (post-randomization) with platelet count $<50 \times 10^9$ and either of these endpoints regardless of whether the patient receives transfusions according to protocol or not. Following conclusion of the study period, transfusion thresholds will be determined by each subject's primary provider.

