Secondary Endpoints	
 (1) Number of eligible patients over a 1-year period (2) Percentage of eligible patients providing consent (3) Progressive or new venous or arterial thrombosis (4) Bleeding events by WHO grade (5) Platelet transfusions (6) PRBC transfusions (7) Transfusion related outcomes (8) Quality of life (FACT-Th18)
Type of control	Institutional standard of care
Trial Blinding	Unblinded
Treatment Groups	A: transfusion threshold of $30 \times 10^9/L$ B: transfusion threshold of $50 \times 10^9/L$
Treatment Schedule	Transfusions will be administered as needed (based upon randomized threshold) throughout a single period of treatment-related thrombocytopenia OR 30 days, whichever is shorter
Number of trial subjects	12
Estimated duration of trial	One year
Duration of Participation	≤ 63 days

ABBREVIATIONS

CT scan	Computed tomography scan
ATE	Arterial thromboembolism
HSCT	Hematopoietic Stem Cell Transplant
SCCA	Seattle Cancer Care Alliance
VTE	Venous thromboembolism
AML	Acute myeloid leukemia
ALL	Acute lymphocytic leukemia
CML	Chronic myeloid leukemia
CLL	Chronic lymphocytic leukemia
MDS	Myelodysplastic syndrome
WHO	World Health Organization
DIC	Disseminated intravascular coagulation
PT	Prothrombin time
PTT	Partial thromboplastin time
V/Q	Ventilation/perfusion scan
APL	Acute promyelocytic leukemia
HLA	Human leukocyte antigen

Contents

1.0 GENERAL INFORMATION	7
1.1 Protocol Title	7
1.2 Sponsor Information	7
1.3 Investigator Information	7
2.0 INTRODUCTION TO THE PROTOCOL	7
2.1 Background and Rationale	7
2.2 Clinical Data to Date	8
2.3 Transfusion Threshold Rationale	9
2.4 Risks/Benefits	9
3.0 OVERVIEW OF CLINICAL TRIAL	10
3.1 Study Objectives	10
3.1.1 Primary Objective	10
3.1.2 Secondary Objectives	10
3.2 Study Population	10
3.3 Study Design	10
3.3.1 Primary Endpoint	10
3.3.2 Secondary Endpoints	11
3.4 Estimated Accrual	11
3.5 Funding Source	11
4.0 SAFETY CONSIDERATIONS	11
4.1 Stopping Rules	11
5.0 SUBJECT ELIGIBILITY	11
5.1 Inclusion Criteria	11
5.2 Exclusion Criteria	12
6.0 Subject Registration	12
7.0 Treatment Plan	13
7.1 Treatment Plan Overview	13
7.2 Baseline/Pre-Treatment Assessment	13
7.3 Randomization	13
7.4 Administration of Transfusions	13
7.5 Concomitant Medication and Supportive Care Guidelines	14
7.5.1 Unfractionated heparin (UFH)	14

7.5.2 Low molecular weight heparin (LMWH)	14
7.5.3 Anticoagulation Dosing Modifications	14
7.6 Transfusion Delays/Modifications	14
7.7 Duration of Therapy	15

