Patients received a median of 6 transfusions over the 30 days following diagnosis, accompanied by both a financial cost and a drain on resources. While cost data were not collected as a part of this study, previous studies have demonstrated increased cost (as high as \$5700/patient in 2014) associated with the use of prophylactic platelet transfusions to target a platelet count of $10 \times 10^9/\text{L}$.⁷ The higher target of $50 \times 10^9/\text{L}$ utilized for most patients in our retrospective study would naturally cost considerably more, in terms of financial cost to the patients, infusion room time and transportation costs (outpatients), prolongation of hospital stays (inpatients) and burden on the finite resource of blood products.

Another relevant issue is that of platelet refractoriness, defined as repeated, inadequate response to platelet transfusions. Rates of platelet refractoriness may be as high as 21.6%

among inpatients requiring platelet transfusions, adding both to the complexity of caring for such patients, particularly if and when bleeding does occur, and to those additional costs mentioned above including monetary (increased mean hospitalization cost of \$66,000 in the year 2000) and resource utilization (17.8 additional units of platelets/patients).⁸

Furthermore, platelet refractoriness may be a sign of the bigger issue of alloimmunization (defined as platelet refractoriness due to antibodies against antigens found in >25% of platelet donors), a major issue among patients undergoing repeated cycles of chemotherapy or stem cell transplant, requiring long term platelet support. Alloimmunized patients require HLA-matched platelet units from matched/directed donors, adding further to the expense and stress on resources. This is a common problem, affecting approximately five patients on the combined leukemia and transplant services at any given time.

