8.2.4 Number of platelet transfusions

Only transfusions administered during the study period will be included. Transfusions administered 'off protocol' or inappropriately while 'on protocol' will also be counted. Type (apheresis unit or pooled packs) and volume of transfusion will also be noted.

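### Recovery in 7.7 needs no minimum time since the last transfusion, and its cut-off is the 50 arm's own trigger, so the outcome window can close earlier in that arm

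*Combined protocol and SAP*

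**What the plan says.** Under 7.7 the study period starts at the first post-randomization count below 50 × 10^9/L. It ends when "the platelet count spontaneously recovers to" a value above 50 "for three consecutive days, in the absence of transfusions", or it runs "for a maximum of 30 days after the date of randomization, whichever is shorter". The rule is the same in both arms and applies "regardless of whether the patient receives transfusions according to protocol or not". No section says how to tell spontaneous recovery from a count raised by transfused platelets, and none reopens the period if the count falls again.

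Section 7.3 states that "patients will receive platelet transfusions on all days when the morning platelet count is below the threshold to which they have been randomized". It asks for daily counts in inpatients and at least three a week in outpatients.

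Several measures depend on the study period:
- Transfusion count (8.2.4): "Only transfusions administered during the study period will be included".
- Daily compliance (8.2.6): judged on the on-protocol days of the period.
- Adverse event recording (10.5): stops when the period ends.
- Primary compliance endpoint: judged at count recovery in the synopsis, and at the end of the study period in 3.3.1.

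After closure, 7.8 and Appendix 2 provide one visit 30 ± 5 days later that takes a bleeding and thrombosis history. Follow-up after broken randomization is not uniform: 7.5.3 and 7.6 run to 30 days from randomization, while 7.7.1 and 9.2 stop at the end of the study period or at count recovery.

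**The concern.** The word *spontaneously* shows that the authors mean the patient's own marrow recovery. The only part of the rule that can be checked from the data is three counts above 50 with no transfusion on those days. In the 30 arm that is a real test, because a patient can go untransfused for days at 35 or 45 without meeting it. In a compliant 50-arm patient with daily counts it is hardly a test: a transfusion-free day already means a count of at least 50.

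If transfusion-supported runs are accepted, observation time depends on the assigned arm. The 50 arm then has fewer days on which transfusions and adverse events are recorded, and fewer days in which to break randomization before compliance is judged. After closure the provider sets the threshold, so the randomized comparison ends as well. Section 3.1.2 wants outcomes reported as they would be in a definitive study, so an arm-dependent window could be carried into that study.

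**Working it through.** **1. The rule in each arm** (7.3 and 7.7; units × 10^9/L)

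| | 30 arm | 50 arm |
|---|---|---|
| Transfuse when count is | below 30 | below 50 |
| Recovery count | above 50 | above 50 |
| Distance between the two | 20 | 0 |
| Three compliant transfusion-free days with daily counts imply | three counts ≥ 30 | three counts ≥ 50 |

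In the 50 arm the last row already meets the numeric condition, except for a count of exactly 50.

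**2. Hand example.** The documents give no platelet kinetics, so these are assumptions. Morning count = own count + residual, where residual(t) = s × [residual(t−1) + increment given]. On day 0 the own count is 40 and the residual 5, so the count is 45 and the 50-arm patient is transfused. The 30-arm patient has own count 40 and no residual, and is not transfused.

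- *Increment 25, s = 0.70, own count flat.* Residuals are 30 × 0.70 = 21.0, then 14.7, 10.3 and 7.2. The 50-arm counts are 61.0, 54.7, 50.3 and 47.2: the window closes on day 3 and the count is below 50 on day 4. The 30-arm patient stays at 40, in the window.
- *Same, own count rising 3 a day.* The 50-arm counts are 64.0, 60.7 and 59.3, closing on day 3 with an own count of 49. The 30-arm counts are 43, 46, 49, 52, 55 and 58, closing on day 6. The gap is 3 days, with no later fall.
- *Increment 15, s = 0.60, own count flat.* Residuals are 20 × 0.60 = 12.0, then 7.2. Counts are 52.0 and 47.2, so the patient is transfused on day 2 and the window does not close.

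The early closure is therefore possible but not inevitable.

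**3. Simulations.** Two day-by-day simulations with daily counts applied the numeric rule literally. All kinetics are assumed.

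| | First | Second |
|---|---|---|
| Scenarios | 18 | 24 |
| Increment | 20–30 | 15–35 |
| Daily survival of transfused platelets | half-life 1.5–3 days, i.e. 0.5^(1/1.5) = 0.63 to 0.5^(1/3) = 0.79 | 0.60–0.85 |
| Own nadir | 5–15, mean 7 or 12 days | 10–20, about 10 days |
| Own rise per day | 2–8 | 3–10 |
| Measurement noise | 6% | 8% |
| Mean window, 30 arm minus 50 arm | 1.9 to 15.2 days | 1.3 to 14 days |
| 50 arm closed with own count < 50 | 50–100% | 15–100% |
| 30 arm closed with own count < 50 | 0–35% | 0–66% |

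The sign was the same in all 42 scenarios. Section 2.2 offers one rough calibration: "Patients received a median of 6 transfusions over the 30 days following diagnosis". Two scenarios of the first simulation match it, with windows of 10.8 against 13.9 days (gap 3.1) and 11.6 against 17.6 days (gap 6.0). In the second, scenarios with about 5 to 7 transfusion days gave gaps of 1.8 to 14 days. With small increments and fast clearance (15, 0.60) the gap was 1.3 to 3.2 days.

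**4. Effect of a transfusion-free interval.** Requiring each counted day to be at least 5 days after the last transfusion cut the gap to between −1.6 and +2.1 days in the first simulation. A 3-day lead-in in the second gave −1.2 to +7.2 days, within 1.3 days either way in 17 of 24 scenarios. These intervals are test values, not proposals. A fixed 30-day window has a gap of zero by construction.

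**5. If a full trial counted bleeding only inside this window.** The plan's power (125 per arm, 40% in both arms, margin 0.16, one-sided 0.05) reproduces closely: Φ(0.16/√(2 × 0.4 × 0.6/125) − 1.645) = Φ(2.582 − 1.645) = 82.6%, against the stated 84%. Now assume a constant hazard with 40% bleeding over W days in the 50 arm and a 30-arm window d days longer. The 30-arm rate is 1 − 0.6^((W+d)/W). For d = 2 this is 44.2% at W = 14 and 42.4% at W = 25, and power falls to 59.6% and 70.5%. For d = 1 power is 72–77%; for d = 3 it is 47–64%. The bias works against the lower threshold, so it costs power and does not create a false non-inferiority claim.

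**The case against.** The best defence is the text itself. Section 7.7 asks for spontaneous recovery, and an assessor may refuse a run carried by the previous day's platelets. A reader might infer that any three-day gap between transfusions in the 50 arm is scored as recovery. The documents do not say that: each count must exceed 50, gaps from delayed or missed transfusions at lower counts do not qualify, and outpatient counts three times a week may not verify three consecutive days at all. The wording permits the scoring; it does not require it. What remains is that, in an unblinded trial, each assessor must supply an unwritten criterion.

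A reader might also infer a known shortening of the 50-arm window. None can be taken from the documents. The range of about 1 to 15 days reflects assumed kinetics and daily counts, and the median of 6 comes from a retrospective cohort in which most, not all, patients were managed to 50.

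A third tempting reading is that the pilot's control-arm bleeding rate must come out too low. The visit in 7.8 still collects later bleeding and thrombosis, so that does not follow. The capture is weaker, though: one contact, dated from an arm-dependent end point, relying on chart review and recall, when 2.2 itself warns that retrospective review misses some bleeds.

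Finally, little in the pilot turns on this. Secondary outcomes are descriptive (13.2), enrolment is unaffected, and 8.2.6 is a percentage that a shorter window does not lower mechanically. With about six patients per arm, 2/6 bleeding has an exact 95% interval of roughly 4% to 78%, far wider than any effect of a few days. The full trial's 40% rests on historical data, and 13.2 does not say that trial would use this window. All of this stands, and it limits the weight of the point without removing it.

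**Conclusion.** The concern holds in a limited form. Cut-off and trigger coincide in the 50 arm only, *spontaneously* has no operational meaning, and no time since the last transfusion is required. A transfusion-supported run can therefore close the 50-arm window before a comparable 30-arm window. The direction was consistent across every scenario examined; the size cannot be fixed from the documents. The transfusion count (8.2.4), adverse event recording (10.5) and compliance judged at recovery or at the end of the study period are most exposed. Bleeding and thrombosis are affected less. No pilot test or sample size changes. The reason to act is that the pilot's descriptive results should compare arms over equal observation time, and the definition should not pass unexamined into a larger trial.

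**What to change.** Count and report transfusions, bleeding, thrombosis and adverse events over one fixed window in both arms, from randomization to day 30. That is the existing cap, and 7.5.3 and 7.6 already use it for some patients. Reconcile 7.7, 7.7.1, 9.2 and 10.5 with it, and state in 7.8 which date the follow-up visit is counted from. Keep the compliance measure in 8.2.6 on on-protocol days. If a recovery date is still reported, or used to judge the primary compliance endpoint, define *spontaneously* by a transfusion-free interval chosen by the investigators and identical in both arms. How transfusions are managed after recovery is for the investigators to reconcile.

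The cost is protocol wording and some extra observation days per patient within the 30-day cap. Some counted days will fall after randomized management has ended, so events on those days should be shown separately as well as in the total. Up to 72 hours before the first count below 50 also enters the window, but under the same rule in both arms.
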